iCBT With TMS in Patients With MDD

NCT05988619 Study protocol with SAP

[name]

Version Date:

29 September 2020

Internet-based Cognitive Behavioral Therapy in Transcranial Magnetic Stimulation

Question: Does the addition of internet-delivered Cognitive Behavior Therapy (iCBT) to TMS improve immediate and long-term symptom, functioning and cognitive outcomes

Background and Significance:

Major Depressive Disorder (MDD) is a common diagnosis, with an estimated lifetime morbid risk of approximately 30% (Kessler et al., 2012). While there are many approaches to the treatment of MDD, current treatments of MDD frequently fail to substantially reduce depressive symptoms among those in need of care, with individual interventions leading to remission in approximately one-third of patients (Trivedi et al., 2006, Rush et al., 2006). Prior research suggests that combining cognitive-behavioral therapy (CBT) and psychopharmacology can produce optimal treatment outcomes compared to the use of either treatment individually (March et al., 2004; Pampallona et al., 2004; Cuijpers et al., 2009).

Non-invasive brain stimulation presents an exciting alternative to these interventions. Transcranial Magnetic Stimulation (TMS) is one especially promising brain stimulation approach used to treat MDD, especially among patients with treatment-resistant symptoms (Diefenbach et al., 2016; Dilkov, et al., 2017). Like psychopharmacological interventions, TMS may produce optimal treatment outcomes when paired with CBT. However, standard TMS protocols are time-intensive, typically requiring daily doctor visits for one hour of six to eight weeks. Therefore, an internet-delivered CBT protocol may augment the effects of TMS without substantially increasing patient burden. To that end, the present study will assess if a combined TMS and internet-delivered CBT protocol may produce superior treatment outcomes compared with TMS alone.

Design:

Randomization to one of two treatments; primary outcomes assessed at

- (a) Baseline
- (b) Post-treatment (6 weeks, or 30 TMS session)
- (c) 8 months after study entrance (~6 months post treatment)
- (d) 11 months after study entrance (~9 months post treatment)

Other measures are collected at baseline, mid-treatment (3 weeks, or 15 TMS session) and post-treatment.

Participants: We will enroll 40 Subjects who will be assigned to iCBT or a mental health video series with 20 enrolled in each group. The same inclusion/exclusion criteria as the TMS clinic will be employed for eligibility. This involves a minimum score of 17 on HAM-D, evidence of treatment resistance, and evaluation by a study investigator. Participants must be right-handed and between 18-70 years of age.

Inclusions: Subjects with Major Depressive Disorder who are receiving a full course of TMS treatment in at the UCLA TMS Clinic. Participants must be willing to undergo 10-Hz TMS treatment at the outset of treatment.

Exclusions: Any indications of metal implants, pregnancy, psychosis, Obsessive compulsive disorder (OCD), autism spectrum disorders, complex regional pain syndromes, substance use dependence and comorbidities that would interfere with treatment response. The criteria are assessed using MINI interview and Hamilton Depression scale conducted by trained and certified interviewers. Participants may not participate if they are currently completing CBT outside of the study.

Eligibility will be determined by TMS physicians who are co-investigators on this study.

Interventions:

RANDOMIZATION	WEEK 1-6
TMS	TMS + Mental Health Television Episode
TMS + ICBT	TMS + ICBT

TMS:

We will evaluate standard of care for TMS, which involves some flexibility but typically includes 6 weeks, five days per week, followed by a weaning from 3 to 1 times per week for the next 3 weeks.

Some flexibility is permitted due to scheduling difficulties; require a minimum of 8 sessions within any given 14 day period during the first six weeks.

Post-treatment will be standardized at 6 weeks (after 30 TMS).

Mental Health Videos or iCBT will occur weekly, according to each participant's schedule. Participants will additionally schedule one weekly coaching session to discuss the viewed material. These coaching sessions will occur via HIPAA-compliant Zoom meetings arranged through the UCLA health system.

Qualitative Electroencephalograph: QEEG will be performed at the UCLA TMS Research area. Recordings will be performed while the subjects are resting in the eye-closed, maximally alert state. Electrodes will be attached to the subjects' scalps either with individual silver chloride electrodes, paste, and nylon electrode cap or net. All of these types of electrodes are non-invasive, apply easily and quickly with little or no discomfort to the subject, and are easily removed with minimal clean up. During the recordings, subjects will either sit in a comfortable chair while the electrodes are applied. The recording will then be performed and the technicians will alert subjects if any signs of drowsiness appear. A CPz-referential montage will be used with electrodes placed according to the 10-20 system (Leuchter et al., 1992; Dunkin et al, 1995). Signals will be digitally recorded (bandpass 0.3-70 Hz) and analyzed. The EEG procedure should not take more than ninety (90) minutes; generally speaking, the actual recording takes about twenty (40) minutes. QEEG studies may be repeated up to three (3) sessions under this protocol, depending upon subject's willingness to record.

Neuropsychological testing: This testing involves completing specific tests measuring cognitive functioning, such as concentration, ability to think, and memory. In addition, subjects may be

asked about their feelings, thoughts, activities, or emotional well-being. Our neuropsychological testing battery may require up to two (2) hours of participation.

iCBT:

Existing standard program (ThisWayUp)

Once per week for weeks 1 through 6.

Plus access to iCBT at other times.

Keep track of usage.

Orientation to program by research staff at first occasion, who will also be available to answer questions (research staff at TMS clinic, who are trained by DGC team- [name])

The protocol for "This Way Up" utilizes the following lesson plan:

Lesson number	Content	Homework exercise
1	Psychoeducation about anxiety and depression, the fight or flight response, controlled breathing, and physical exercise	Controlled breathing, physical exercise
2	Cognitive therapy components: education about the cognitive model, cognitive distortions, and introduction to thought monitoring; activity planning	Thought monitoring, activity planning
3	Thought challenging/cognitive restructuring; challenging positive and negative metacognitive beliefs about repetitive negative thinking; shifting attention, hunt for positives	Thought challenging, hunt for positives
4	Education about avoidance and safety behaviors; graded exposure and structured problem solving	Graded exposure and structured problem solving
5	Advanced graded exposure (imaginal exposure, interoceptive exposure); troubleshooting difficulties with graded exposure	Graded exposure
6	Relapse prevention	Relapse prevention plan

Lesson content is presented in the form of an illustrated story about two fictional characters who are anxious and depressed, but who gain mastery over their problems using CBT techniques. Following each lesson, participants download a document that summarizes the key information in each lesson, and includes practical homework exercises that reinforce the content of the lesson. Participants are encouraged to practice their lesson homework for at least 2 hours in the 3-4 days before starting the next lesson.

Participants also have access to:

- 1) frequently asked questions about each lesson
- 2) "Patient Recovery Stories" from former patients, and
- 3) extra resources on a range of topics such as sleep hygiene, medications and panic attacks.

Once participants download their homework, they will be considered to have completed the lesson. Lessons will be completed sequentially. "This Way Up" will be hosted locally on our secure server and can be directly accessed via the website <https://ucla.thiswayupclinic.com/>.

The "This Way Up" program is hosted on the Semel-NPI server architecture. After being registered by a study clinician, participants log-in to access lesson content only, no identifiable e-mail other than name and e-mail are stored in the system.

Mental Health Television Episodes

The existing program, Stories of the Mind, was originally developed for the Public Broadcast Service (PBS) and affiliated broadcasts. It is freely available at <http://mentalhealthchannel.tv/series/stories-of-the-mind>.

Participants will view a video once per week for weeks 1 through 6. Although they have access to all videos of the program, they will be specifically instructed to view materials according to the following schedule:

Lesson number	Episode Title	Episode Description
1	Overcoming Depression	A writer, a musician and a video blogger find three surprising paths to recovery, with powerful takeaways for all viewers.
2	Beating Anxiety	Three characters in different times of their lives use different tactics to manage their anxiety, the most common type of mental health disorder for Americans.

3	Get your Sleep	Sleep deprivation affects everything, from memory to mood to decision making. In our 36-hour No Sleep Challenge, researchers track 4 participants to see just how vital sleep is to your mental health.
4	Coping with Illness	When your physical health suffers, your mental state may too. Meet three people who practice good mental health despite physical conditions.
5	A Place to Belong	Being part of a strong community is good for anyone's mental health.
6	Ways to Wellness	Five ways for every viewer to achieve optimum mental fitness, told through the personal experiences of fascinating, diverse characters.

Study Schedule:

TMS + iCBT Group	Baseline	Week 1	Week 2	Week 3	Week 4	Week 5	Week 6	Weeks 7-9	6 Month F/U	9 Month F/U
Consent	X									
TMS		5x	5x	5x	5x	5x	5x	1-5x per week		
iCBT Access and Coaching		1x	1x	1x	1x	1x	1x			
EEG	X			1x			1x			
Stroop	X									
HAMD	X								X	X
IDS	X								X	X
DARS	X								X	X
GAD-7	X								X	X
Sheehan	X								X	X
Pt Attitude and Expectancy Form	X									
Demographics	X									
Medical Status	X	X	X	X	X	X	X	X	X	X
TMS + Mental Health Videos	Baseline	Week 1	Week 2	Week 3	Week 4	Week 5	Week 6	Weeks 7-9	6 Month F/U	9 Month F/U
Consent	X									
TMS		5x	5x	5x	5x	5x	5x	1-5x per week		
Video Access and Coaching		1x	1x	1x	1x	1x	1x			
EEG	X			1x			1x			
Stroop	X									
HAMD	X								X	X
IDS	X								X	X
DARS	X								X	X
GAD-7	X								X	X
Sheehan	X								X	X
Pt Attitude and Expectancy Form	X									
Demographics	X									
Medical Status	X	X	X	X	X	X	X	X	X	X

The frequency of follow-up assessments may be modified depending on patient availability, or subject willingness to undergo more or less assessment.

Primary Dependent Measures:

The primary analyses for this study will involve multilevel modeling of longitudinal data over the course of treatment (e.g. baseline, mid-assessment, post-assessment). We hypothesize that the iCBT + TMS will demonstrate more rapid improvement in these five symptom scales compared with TMS alone.

In addition, secondary analyses will involve multilevel modeling of symptom score relapse (e.g. baseline, end of treatment, 6 months post-treatment, 9 months post-treatment). We hypothesize that iCBT + TMS will demonstrate more lasting change in these five symptom scales compared with TMS alone, such that the combined treatment reduces the likelihood of symptom relapse.

Finally, analyses will assess changes in cognitive functioning during the course of treatment, using a electroencephalography (baseline, mid-assessment) and a well-validated Stroop Task (baseline and post-treatment). Changes in cognitive functioning will be assessed with multilevel modeling in parallel to the primary analyses above as a means of exploring whether changes in cognitive functioning coincide with changes in treatment.

Symptom Scales:

HAM-D (baseline, mid, post, 6 months)

IDS (Inventory for Depression Symptomatology) (weekly from baseline to end of TMS, and at 6 month and 9 month follow-up)

DARS (Dimensional Anhedonia Rating Scale) (baseline, mid, post, 6 months, 9 months)

GAD-7 (baseline, mid, post, 6 months, 9 months)

Functioning Scale:

Sheehan Disability scale (baseline, mid, post, 6 months, 9 months)

Cognitive Functioning:

EEG (baseline, mid)

STROOP (baseline, post)

Additional Measures:

Patient Attitude and Expectancy Form

Demographics and medical status

Modified intent-to-treat analyses will be conducted using linear multilevel modeling in Stata 18.0 using the *mixed* function. All models include random effects of the intercept and fixed slopes for each participant. Group will be included as a categorical variable in all analyses. Time will be included as a continuous variable in primary analyses, with secondary analyses including Time as a categorical variable to evaluate pairwise Group comparisons. Age (continuous) and Gender (categorical) will be included in all analyses as covariates.

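### IDS is scored weekly on treatment, but the plan does not say which of those scores enter the primary model, so the IDS visit set and its residual structure are left open

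*Combined protocol and SAP*

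**What the plan says.** Under Primary Dependent Measures, one primary analysis covers HAM-D, IDS, DARS, GAD-7 and Sheehan: "multilevel modeling of longitudinal data over the course of treatment (e.g. baseline, mid-assessment, post-assessment". Its hypothesis concerns speed: "We hypothesize that the iCBT + TMS will demonstrate more rapid improvement in these five symptom scales compared with TMS alone".

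The measures list below it (Symptom Scales and Functioning Scale) gives the other four scales at baseline, mid and post during treatment. IDS alone is collected "weekly from baseline to end of TMS, and at 6 month and 9 month follow-up".

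The closing analysis paragraph sets the model for every scale: "All models include random effects of the intercept and fixed slopes for each participant", and "Time will be included as a continuous variable in primary analyses". It names no residual correlation structure and no list of IDS visits.

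Timing comes from two other places. Design says "Other measures are collected at baseline, mid-treatment (3 weeks, or 15 TMS session) and post-treatment". The TMS section says "Post-treatment will be standardized at 6 weeks (after 30 TMS", but it also describes about three further weeks of tapering TMS, and the Study Schedule tables show TMS in weeks 7 to 9. Both of those tables mark IDS only at baseline and at the two follow-ups. The rows for the other four scales look the same.

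**The concern.** The only visits named for the primary model are the three that all five scales share. A statistician could fit IDS on those three, or on every on-treatment score, and be faithful to the plan either way. The two fits can give different estimates and p-values, so the primary IDS result is not fixed before the data are seen.

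Two further things depend on the choice. IDS is the one scale with weekly data on rate of change, and a trial of 40 has little precision to give away. In addition, scores a week apart are likely to be more alike than a random intercept alone allows for. A model that is nearly adequate for visits three weeks apart may therefore understate the error for weekly visits.

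**Working it through.** **Inputs from the documents.** 20 participants per arm; mid at week 3; post at week 6; IDS weekly; random intercept with a fixed linear slope. The plan states no power, SD, within-patient correlation or effect size, so there is no figure of its own to reproduce.

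**Assumptions.** The end of TMS is week 6, giving seven scores. The total SD is 1 and there is no dropout. ICC is 0.5 where needed. Where serial correlation is considered, residuals are AR(1) at 0.3 to 0.6 per week.

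**1. Precision under the stated model.** With n per arm, the slope contrast has variance (2/n) × σ²/Sxx, where Sxx is the sum of squared deviations of the visit times from their mean.

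- Weeks 0, 3, 6: Sxx = 9 + 0 + 9 = 18.
- Weeks 0 to 6: Sxx = 2 × (9 + 4 + 1) = 28.
- SE ratio, three visits to seven: √(28/18) = 1.247.
- Information ratio: 18/28 = 0.643, a loss of 36%.

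These ratios do not depend on n, SD or ICC.

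**2. What that means in power.** The residual variance is 0.5. The SE of the week-6 difference is 6 × √((2/20) × 0.5/18) = 0.316 SD with three visits and 6 × √((2/20) × 0.5/28) = 0.254 SD with seven. For an assumed difference of 0.8 SD that builds linearly to week 6 (two-sided 0.05), z is 2.53 against 3.16, so power is 72% against 88%.

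**3. The same comparison with other correlation structures.** Generalised least squares, with the structure modelled correctly:

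| Structure (assumed) | SE, three ÷ seven visits | Power at 0.8 SD, ICC 0.5: three vs seven |
|---|---|---|
| Independent residuals | 1.25 | 72% vs 88% |
| AR(1), 0.3 per week | 1.08 to 1.09 | 72% vs 78% |
| AR(1), 0.6 per week | about 1.01 | 74% vs 75% |

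If individual slopes also vary (SD 0.05 to 0.15 per week, ICC 0.3 to 0.7), the ratio is about 1.09 to 1.23. The plan's model has no such term.

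**4. Missing week 6.** Under independent residuals, a participant without a week-6 score contributes Sxx = 2 × 1.5² = 4.5 from weeks 0 and 3. Weeks 0 to 5 would give 2 × (2.5² + 1.5² + 0.5²) = 17.5.

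**5. Weekly scores in the stated model, unchanged.** With balanced visits, the random-intercept fit gives the ordinary least-squares slope. Let c be the centred times and R the AR(1) correlation matrix. The true slope variance is proportional to c′Rc/Sxx². The model reports s²/Sxx, where s² is the mean within-patient variance. The true SE divided by the reported SE is therefore √[(c′Rc/Sxx)/s²], and the large-sample type I error is 2 × [1 − Φ(1.96 ÷ that ratio)].

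| Visits | AR(1) per week | c′Rc/Sxx | s² | SE ratio | Type I error |
|---|---|---|---|---|---|
| 7 | 0.3 | 38.05/28 = 1.359 | 0.886 | 1.24 | 11% |
| 7 | 0.6 | 43.77/28 = 1.563 | 0.674 | 1.52 | 20% |
| 3 | 0.3 | 17.99/18 = 0.999 | 0.982 | 1.01 | 5% |
| 3 | 0.6 | 17.16/18 = 0.953 | 0.840 | 1.07 | 7% |

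The intercept variance cancels, so these rates are the same at ICC 0.3, 0.5 or 0.7.

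**The case against.** A reader might infer that the plan discards four of seven IDS scores. The documents do not support that. The three visits are introduced as examples, no text limits the IDS model to them, and a mixed model with continuous time accepts weekly scores as they stand. The sentence in Design about other measures does not help the stronger reading. It describes collection, not analysis, and if it did cover IDS it would contradict weekly collection.

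Weekly collection is itself not fully settled, because the schedule tables show no on-treatment IDS. Those tables omit on-treatment ratings for all five scales, so they look incomplete and do not refute the measures list, but they do conflict with it. The count of seven also rests on reading the end of TMS as week 6. If the tapering weeks count, there could be up to ten scores.

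It is also fair to say that the 25% figure is a best case. It assumes independent weekly residuals, and under the serial correlation considered here most of the gain disappears. Nor is IDS the only scale that can address speed of improvement, since a linear slope is identified from three visits on any of the five.

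All of this stands, and it limits the claim about lost precision. It does not answer the point that the visit set is open, or that simply adding the weekly scores to the stated model would carry a cost of its own.

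**Conclusion.** The concern holds as an uncommitted choice, not as a documented loss of data. Both unqualified routes have a drawback. Modelled correctly, three visits are never more precise than seven, and the penalty runs from about 1% to 25% in the slope standard error, depending on a correlation that the plan does not give. Seven visits in the model as written could give about 11% to 20% type I error in place of 5%, if weekly residuals are serially correlated at 0.3 to 0.6. These error rates are large-sample approximations for complete data.

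The case for naming the visits in advance does not depend on where in these ranges the truth lies. The point affects IDS only; the other four scales have no weekly data. It should be corrected before analysis, but it does not undermine the design.

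**What to change.** In Primary Dependent Measures and the closing analysis paragraph, state that:

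- the primary IDS model uses every weekly score from baseline to week 6;
- Time in that model is actual weeks since baseline;
- its residual structure allows serial correlation, for example AR(1), or the continuous-time equivalent if visits do not fall on whole weeks;
- HAM-D, DARS, GAD-7 and Sheehan keep baseline, mid and post.

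In the measures list, define what the end of TMS means for IDS collection: the week-6 assessment, or the end of the tapering weeks. Then reconcile the Study Schedule tables with the measures list so that both show the same on-treatment ratings.

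The cost is a few sentences and a table correction, with no visits beyond those already in the measures list. The IDS model gains one covariance parameter, and the gain in precision may turn out to be modest.

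### EEG is scheduled at baseline, week 3 and week 6 in both arms, but the analysis text and the measures list name only baseline and mid-treatment; the two should be reconciled.

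*Combined protocol and SAP*

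**What the plan says.** Three places fit three EEG time points:

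- **Study Schedule.** The EEG row is marked at baseline, week 3 and week 6, identically in the two arm tables.
- **Qualitative Electroencephalograph.** "QEEG studies may be repeated up to three (3) sessions under this protocol, depending upon subject's willingness to record". Three sessions are allowed but not guaranteed.
- **Design.** "Other measures are collected at baseline, mid-treatment (3 weeks, or 15 TMS session) and post-treatment".

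Two places name only two:

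- **Primary Dependent Measures**, paragraph on cognitive analyses. Change is to be assessed "using a electroencephalography (baseline, mid-assessment) and a well-validated Stroop Task (baseline and post-treatment".
- **Cognitive Functioning** list. The EEG entry is "EEG (baseline, mid" and stops there. The Stroop entry beside it is "STROOP (baseline, post".

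The paragraph on cognitive analyses describes them as exploratory. It says that they cover the course of treatment and run in parallel to the primary symptom models, whose time points are baseline, mid and post. The TMS section fixes post-treatment at week 6. The closing analysis paragraph specifies random intercepts, fixed slopes and, in primary analyses, continuous time. No passage explains why week 6 is absent from the EEG analysis.

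**The concern.** A reader cannot tell whether a week-6 EEG is to be recorded, or whether it would be analysed if it were. If the schedule governs data collection and the analysis text governs the model, participants give a third recording (a procedure of up to 90 minutes) that has no stated use. The EEG analysis then stops halfway through the six-week course.

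Two comparisons suffer. EEG change would be measured over weeks 0 to 3 and Stroop change over weeks 0 to 6, so the two cognitive measures would share only baseline. EEG change could be set against symptom change to mid-treatment but not to the end of treatment, although the stated purpose is to see whether cognitive change coincides with change during treatment. Leaving the point open also allows the set of EEG visits to be chosen after the data have been seen.

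**Working it through.** The plan gives no power, effect size or EEG count, so there is no figure of its own to reproduce.

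**1. Recordings affected.** The Participants section gives 40 participants, 20 per arm.

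- Scheduled: 40 × 3 = 120.
- Named in the analysis: 40 × 2 = 80.
- Not named: 40, or 40/120 = 33.3%.

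The one-third share is a ceiling, because repeat sessions depend on willingness. With complete baseline and mid recordings and an assumed week-6 completion *p*, the unused share is 40*p*/(80 + 40*p*): 31%, 29%, 26% and 20% for *p* = 0.9, 0.8, 0.7 and 0.5.

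**2. Visits shared with other measures, by the text lists.**

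| Measure | Baseline | Mid | Post |
|---|---|---|---|
| EEG, analysis text and list | yes | yes | no |
| EEG, Study Schedule | yes | yes | yes |
| Stroop, list | yes | no | yes |
| Symptom scales, lists | yes | yes | yes |

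As written, EEG shares one visit with Stroop and two with the symptom scales. With week 6 added it shares two and three.

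**3. Precision of the weekly slope.** Assume that the EEG model follows the primary form (random intercept, linear time). With 20 per arm and residual standard deviation σ, the standard error of the group difference in slope is √(2σ²/(20·Sxx)), where Sxx is the sum of squared deviations of the visit times.

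- Weeks 0, 3: Sxx = 1.5² + 1.5² = 4.5; SE = 0.149σ per week.
- Weeks 0, 3, 6: Sxx = 3² + 0² + 3² = 18; SE = 0.075σ per week.

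The ratio is √(18/4.5) = 2. Two departures reduce it:

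- *Incomplete week 6* (within-person information only): mean Sxx is 18*p* + 4.5(1 − *p*). At *p* = 0.8 this is 15.3, ratio 1.84; at *p* = 0.5 it is 11.25, ratio 1.58.
- *Serial correlation*: under an assumed AR(1) correlation of 0.3, 0.5 or 0.7 between adjacent visits, the ratio is 1.75, 1.63 or 1.53.

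**4. Does the smaller standard error mean more power?** The detectable slope difference at 80% power (two-sided 5%, both assumed) is SE × (t₀.₉₇₅ + t₀.₈₀). The multiplier is 2.876 on 38 df (40 × 1 − 2) for two visits and 2.837 on 78 df (40 × 2 − 2) for three. The within-person variance is not in the documents, so a range is shown, in units of total SD.

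| Within-person variance | Two visits, per week | Three visits, per week | Two visits, over 3 weeks | Three visits, over 6 weeks |
|---|---|---|---|---|
| 0.3 | 0.235 | 0.116 | 0.70 | 0.69 |
| 0.5 | 0.303 | 0.150 | 0.91 | 0.90 |
| 0.7 | 0.359 | 0.177 | 1.08 | 1.06 |

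Per week, the detectable difference halves. Over the window that each design observes, it hardly changes. The reason is that week 3 is the mean of 0, 3 and 6 and has no weight in the linear slope, so the gain comes from the longer span.

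Let D₃ and D₆ be the true group differences in change at weeks 3 and 6. The expected slopes are D₃/3 and D₆/6. With the standard error halved, the ratio of signal to noise, three visits against two, is (D₆/6)/(SE/2) ÷ (D₃/3)/SE = D₆/D₃. It is 2 if the difference grows linearly, 1 if it levels off at week 3, and below 1 if it shrinks afterwards.

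**The case against.** The strongest objection is that nothing in the documents says a week-6 EEG will be taken and then thrown away. The Cognitive Functioning entry stands among lists that give assessment times for every measure, so it may mean that only two EEGs are planned and the schedule is wrong. This stands. A reader might infer that the plan discards a third of the EEG data from every participant. The documents do not support that: what they show is a contradiction, the third session depends on willingness, and one third is the largest planned share rather than a known loss.

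The alignment argument also draws on two sources that disagree. The week-6 EEG comes from the schedule tables, yet those tables show Stroop at baseline only and no mid- or post-treatment visits for the HAMD, IDS, DARS, GAD-7 or Sheehan. The post-treatment Stroop and symptom scores come from the text lists. This stands too, and is a reason to reconcile the tables as a whole. It does not remove the EEG conflict, because the Design and Qualitative Electroencephalograph sections independently fit three EEG time points.

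Finally, the halved standard error invites the reading that power is being given away. That holds only if the group difference in EEG keeps growing after week 3, which no passage states.

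**Conclusion.** The inconsistency is real and should be resolved. Three parts of the document fit three EEG time points, two name only two, and the difference is not explained. The two-point version also sits badly with the plan's own aim of covering the course of treatment in parallel to models that run to week 6.

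If the schedule is followed and the analysis is run as written, the consequence is up to 40 unused recordings and an EEG window of half the treatment course. The two-visit standard error of the weekly slope would be 2 times the three-visit one under the random-intercept, linear-time form with full completion, and about 1.5 to 1.75 times under the assumed AR(1) correlations. What that is worth in power depends on D₆/D₃, which is unknown.

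The more secure argument for including week 6 is coverage: by the text lists, it is the only EEG that can be set against post-treatment Stroop and symptom scores. The stakes are limited, since the EEG analysis is exploratory and the primary symptom comparison does not use it.

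**What to change.** Add the post-treatment time point to the EEG entry in both places (the paragraph on cognitive analyses and the Cognitive Functioning list), and state that the exploratory EEG multilevel model will use all available scheduled recordings. This agrees with the Design section, the Qualitative Electroencephalograph section and the Study Schedule. If only two EEGs are intended, remove the week-6 EEG from both schedule tables and give the reason. Make the choice before EEG data are examined.

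In the same revision, bring the Stroop and symptom-scale rows of the schedule tables into line with the text lists.

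If the schedule is what is being followed, the cost is a line of wording and the processing of recordings already planned. If the two-point text reflects actual practice, adding week 6 would mean up to 40 further recordings of up to 90 minutes each, and the sponsor should weigh that against an exploratory aim.
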